12.1.8. Exploratory Analyses

Analyses of indices

- We will calculate the ICC for absolute agreement (two-way, mixed effect) between the PSG and DreamKit ODI3%, total respiratory events, total apneas, total hypopneas, total obstructive apneas, total central apneas, and total mixed apneas, along with 95% CIs.
- We will construct a confusion matrix and calculate Cohen's kappa (linear weighted) for four categories of disease severity determined by the PSG and DreamKit (AHI 0-4.9, 5-14.9, 15-29.9, and ≥ 30 events/hour).
- We will construct a confusion matrix depicting true-positives, false-positives, true-negatives, and false-negatives for the AHI, CAI, and ODI3% (separately) at thresholds of 5, 15, 20, 30, and 40 events/hour.
- We will calculate the accuracy (percentage agreement between PSG and DreamKit), sensitivity, specificity, positive predictive value, negative predictive value, positive likelihood ratio, and negative likelihood ratio for each threshold of the above indices.
- We will construct a receiver operating characteristic curve and calculate the area under the curve for each threshold of the above indices.
- We will construct a Bland-Altman plot for each threshold of the above indices, including a 95% CI for the upper and lower limits of agreement.

Document ID:	SRC_SLE_Sparkle_PSG_2020_10908	Document title:		Classification:	Confidential
Modified:	26 July 2021	Clinical Investigation Protocol ICH E6 Aligned			
Version:	5	User Tool ID:	16.2.6UserTool0004		
Status:	Final	User Tool Version Date	5June2019	Page:	38

- We will construct a scatter plot with regression line for each threshold of the above indices.
- We will repeat all analyses listed above using the AASM alternative hypopnea criteria.

Event-level analyses

- We will construct a 2x2 confusion matrix based on the presence/absence of events by adapting the methodology described in the AASM Inter-Scorer Reliability Program: Respiratory Events (2014).¹⁶ Each epoch staged as sleep per the PSG will be deemed ‘positive’ if it contains at least one respiratory event of any type, and ‘negative’ if it contains no respiratory events/s.
- We will construct a 4x4 confusion matrix based on apnea differentiation (obstructive apnea, central apnea, mixed apnea, no event), following the above methodology using events staged as sleep per the PSG, and calculate Cohen’s kappa.¹⁷ In cases where a single epoch contains more than one event, the first event will be used for categorization. Mixed events will be categorized independently if we observe at least five mixed events/hour in at least 5% of participants and at least ten mixed events/hour in at least 2% of participants in the evaluable dataset; otherwise, mixed events will be placed in the obstructive category to create a 3x3 confusion matrix.

Signal quality analyses

- Finally, we will compare the average percentage of useable signal quality from the DreamKit respiratory effort signal (PARE algorithm) and PSG (thoracic and/or abdominal belts).

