4.5. Considerations regarding study endpoints

4.5.1. Rationale for the selection of endpoints

The table below summarizes the respiratory parameters required to be reported for HSATs in clinical settings, per the AASM Scoring Manual (Version 2.6). We prioritized the AHI and CAI for our primary and secondary hypotheses, respectively, and included all other listed variables in our exploratory analyses.

Table 1: AASM reporting requirements for adult HSAT reports

Parameter	AASM Reporting Requirement	Endpoint
Respiratory event index* (REI); events/hour	Recommended	Primary (continuous) Exploratory (4-category and binary)
CAI; events/hour	Optional	Secondary (continuous) Exploratory (binary)
Number of respiratory events	Recommended	Exploratory (continuous)
Number of apneas	Recommended	Exploratory (continuous)
Number of hypopneas	Recommended	Exploratory (continuous)
Number of obstructive apneas	Optional	Exploratory (continuous)
Number of central apneas	Optional	Exploratory (continuous)
Number of mixed apneas	Optional	Exploratory (continuous)
A measure of SpO ₂ saturation:	Recommended	Exploratory (continuous) [based on ODI3%]
• ODI3% or ODI4%		
• SpO ₂ Mean/maximum/minimum		
• Percentage of time <88% or other SpO ₂ threshold		

The AASM scoring manual (Version 2.6) Section IX, Part 1, stipulates that recommended parameters must be reported, and that optional parameters may be monitored at the discretion of the clinician or investigator and if monitored, should be reported.

* Throughout this document, we refer to the AHI rather than the REI, as the DreamKit includes a measurement of sleep (see Section 8.1.5).

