8.1.5. Data processing and scoring

All data processing will take place at Philips using Sleepware software. The analyst will import the DreamKit and PSG signals, ensuring that the signals are mapped correctly. The analyst will then inspect the time alignment of the DreamKit and PSG signals; if necessary, the DreamKit time may be adjusted to ensure synchronization with the PSG pulse rate and/or flow signal/s recorded from the shared nasal cannula.

Automated scoring using Somnolyzer will be used for PSG and DreamKit respiratory event detection within the rest period (time between lights off and lights on). Sleep staging during the rest period will be undertaken using Somnolyzer (PSG) or CReSS (DreamKit) algorithms. Sleep staging and event scoring will follow AASM guidelines.¹⁴ Apneas will be scored when there is a ≥90% reduction in airflow for at least ten seconds (Section IX Part 1, G1), and classified as obstructive (continued or increased respiratory effort throughout), central (absence of respiratory effort throughout), or mixed (initial absence followed by resumption of respiratory effort). For our primary and secondary analyses, hypopneas will be scored according to the AASM recommended criteria; that is, a ≥30% reduction in airflow for at least ten seconds, associated with a SpO₂ desaturation of ≥3% (Section IX Part 1, H1A). We will perform a sensitivity analysis in which hypopneas are scored according to the alternative criteria (a ≥30% reduction in airflow for at least ten seconds, associated with a SpO₂ desaturation of ≥4%; Section IX Part 1, H1B).

The following metrics will be calculated for both the PSG and DreamKit:

- AHI: Number of apneas and hypopneas divided by TST;
- CAI: Number of central apneas divided by TST;
- ODI: Number of SpO₂ desaturations (≥3%) divided by TST.

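### Event-level matrices limited to PSG-sleep epochs leave out DreamKit events in PSG wake that still count in the DreamKit-AHI, so event-level PPV is favoured

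*Combined protocol and SAP*

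**What the plan says.** Section 12.1.8 (Event-level analyses) plans two exploratory tables.

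- The 2x2 table of event presence: "Each epoch staged as sleep per the PSG will be deemed" positive or negative according to whether it contains a respiratory event of any type. No summary statistic is named for it.
- The 4x4 table of apnea type, which collapses to 3x3 if mixed events are rare, is built "following the above methodology using events staged as sleep per the PSG". Cohen's kappa is named for this one.

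Section 8.1.5 defines the inputs differently.

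- Detection: "Automated scoring using Somnolyzer will be used for PSG and DreamKit respiratory event detection within the rest period", that is, from lights off to lights on.
- Staging: "Sleep staging during the rest period will be undertaken using Somnolyzer (PSG) or CReSS (DreamKit) algorithms".
- Index: "The following metrics will be calculated for both the PSG and DreamKit", starting with "AHI: Number of apneas and hypopneas divided by TST".

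Section 4.5.1 explains the use of AHI rather than REI by noting that "the DreamKit includes a measurement of sleep". No section limits the DreamKit-AHI numerator to PSG sleep, says whether DreamKit events in CReSS-wake epochs are kept or removed, or plans an event-level table on any wider set of epochs.

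**The concern.** The comparator's sleep staging decides which DreamKit errors can be seen in the event-level tables. The DreamKit-AHI, which feeds the primary endpoint, is not filtered in that way. If CReSS calls an epoch sleep, the PSG calls it wake, and DreamKit scores an event there, the event raises the DreamKit-AHI and enters neither table.

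The intended use statement in Section 4.4 says the device provides what is needed to detect apneas and hypopneas and to classify them. The two event-level tables are the only planned analyses that check whether individual events match. Totals and indices reflect extra events but cannot locate them, and missed and false events can cancel in a total. A reader who derives PPV from the 2x2 table would get a figure more favourable than DreamKit achieves with its own staging. Nor could the table explain AHI disagreement that arises in mis-staged wake.

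**Working it through.** The plan gives no performance figure for the event-level tables, so there is nothing to reproduce. The check is algebra for direction, then an illustration for size.

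**Direction.** Let TP, FP, FN and TN be the counts in PSG-sleep epochs. Add A epochs that the PSG calls wake and CReSS calls sleep, of which x carry a DreamKit event. Treat PSG wake as reference-negative.

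- Sensitivity = TP/(TP+FN). No added epoch is reference-positive, so it does not change.
- PPV goes from TP/(TP+FP) to TP/(TP+FP+x). It falls whenever x > 0.
- Specificity goes from TN/(TN+FP) to (TN+A−x)/(TN+FP+A). It falls only if x/A exceeds FP/(TN+FP), that is, if DreamKit's event rate in these epochs exceeds its false-positive rate in PSG sleep. Otherwise it is unchanged or rises, because true negatives are added too.

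**Size (all rates assumed).** An 8-hour rest period has 960 thirty-second epochs. A share w is PSG wake (15% or 25%), CReSS stages a share m of that wake as sleep (30% or 60%), and a share e of those epochs carries a DreamKit event. In PSG sleep, 30% of epochs are positive, sensitivity is 85% and specificity 95%.

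- w = 0.15: 816 sleep epochs; TP = 0.85 × 0.3 × 816 = 208.08; FP = 0.05 × 0.7 × 816 = 28.56.
- w = 0.25: 720 sleep epochs; TP = 183.6; FP = 25.2.
- Restricted table, either w: PPV = 208.08/236.64 = 0.879, specificity 0.950, 2x2 kappa 0.808.

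Either-sleep table:

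| w, m, e | added epochs (960wm) | unseen FP | PPV | specificity | 2x2 kappa |
|---|---|---|---|---|---|
| 0.15, 0.3, 0.10 | 43.2 | 4.3 | 208.08/240.96 = 0.864 | 0.946 | 0.800 |
| 0.25, 0.6, 0.30 | 144 | 43.2 | 183.6/252 = 0.729 | 0.894 | 0.705 |
| 0.25, 0.6, 0.05 | 144 | 7.2 | 0.850 | 0.950 | 0.800 |
| 0.25, 0.6, 0.02 | 144 | 2.9 | 0.867 | 0.957 | 0.812 |

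The first two rows are the ends of the range for e from 10% to 30%. The last two show what happens when e equals or falls below the 5% false-positive rate in sleep. Specificity is then unchanged or higher, and at 2% kappa is slightly higher as well. PPV is lower in every row. The kappa here is for the 2x2 table and is illustrative only, since the plan names kappa for the apnea-type table.

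**Wider check.** A second grid added all PSG-wake epochs: 120 to 360 wake epochs, prevalence 5–50%, sensitivity 70–90%, false-positive rate 2–10% in sleep and 0.5–20% in wake. That gives 4 × 5 × 3 × 3 × 7 = 1,260 scenarios. The PSG-sleep restriction overstated PPV in all 1,260 and never changed sensitivity. It overstated specificity in 540 and understated it in 540. It overstated accuracy in 460 and understated it in 768. It overstated kappa in 843 and understated it in 417.

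**The case against.** The strongest reply is that the PSG-sleep frame is a reasonable choice. It separates event detection from sleep-staging error, and Section 12.1.8 says it adapts a published inter-scorer method. That stands, and the existing tables should stay. It does not remove the need for a second view, because two separate algorithms stage sleep here.

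A reader might infer that the restriction overstates event-detection performance as a whole. The documents do not support that. Sensitivity is untouched, and specificity, accuracy and kappa can move either way with rates that the plan does not give. An illustration that sets the event rate in mis-staged wake above the false-positive rate in sleep builds the fall in specificity into its assumptions. There may also be an opposite effect. If DreamKit events in CReSS-wake epochs are removed, event-positive epochs that the PSG calls sleep and CReSS calls wake become false negatives against the device. The plan is silent on this.

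A reader might also infer that errors are hidden from the main result. They are not. These events still reach the AHI ICC, the Bland-Altman plots and the exploratory ICCs for "total respiratory events, total apneas, total hypopneas, total obstructive apneas, total central apneas, and total mixed apneas".

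Finally, a DreamKit event in PSG wake need not be spurious as a breathing event. Section 8.1.5 runs detection for both systems over the rest period, and Section 8.1.3 has them share one nasal cannula. Treating PSG wake as reference-negative is a convention that the SAP should state.

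**Conclusion.** The point holds in a limited form. Both event-level tables exclude DreamKit events in epochs that the PSG calls wake and CReSS calls sleep, although those events count in the DreamKit-AHI. With PSG wake taken as reference-negative, this understates the false-positive count and favours PPV whenever such events occur. Specificity is favoured only if DreamKit's event rate in those epochs exceeds its false-positive rate in PSG sleep. Kappa may be favoured too, but can also move the other way.

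In the illustration with e between 10% and 30%, the restricted PPV of 0.88 compares with 0.86 to 0.73 on the wider frame. That range rests wholly on assumed rates. The analyses are exploratory and Hypotheses 1 and 2 do not depend on them, so this is an inexpensive improvement to the plan and does not put the study's conclusions at risk.

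**What to change.** In Section 12.1.8:

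1. Keep the PSG-sleep 2x2 and 4x4 (or 3x3) tables as planned.
2. Add companion tables over epochs staged as sleep by either the PSG or DreamKit, with PSG-wake epochs as reference no-event.
3. Report the number of DreamKit events in PSG-wake epochs.

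In Sections 8.1.5 and 12.1.8, state how DreamKit events in CReSS-wake epochs are handled, with the same rule for the AHI numerator and for the tables.

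The cost is SAP wording and one more tabulation from files already collected. The downside for the sponsor is a possibly less favourable event-level PPV or kappa.

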4.3. Exploratory Analyses

Exploratory analyses will include investigating reliability of the 3% oxygen desaturation index (ODI3%), total respiratory events, total apneas, total hypopneas, total obstructive apneas, total central apneas, and total mixed apneas; agreement of the AHI categorized according to American Academy of Sleep Medicine AASM thresholds for mild/moderate/severe SDB; diagnostic performance metrics at clinically-relevant thresholds of the AHI, CAI, and ODI3%; event-level differentiation of events; and a comparison of signal quality between the DreamKit and PSG. The primary and secondary analyses will adopt the AASM recommended criteria for identifying hypopneas; in exploratory analyses we will also investigate the impact of using the alternative criteria.

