4.4. Claims and Intended Performance

The proposed intended use statement for DreamKit is as follows, with the parts relevant to this study bolded (wording may change before regulatory submission):

*The DreamKit device is a physiologic data recorder intended to collect and record data for use by clinical software used in polysomnography and sleep disorder studies **for the diagnosis of sleep related breathing disorders**. The Plethysmography-Acquired Respiratory Effort (PARE) algorithm provides a respiratory effort signal acquired from the DreamKit photoplethysmography signal that correlates with traditional respiratory effort signals used in polysomnography. The DreamKit with PARE provides the information required to **detect apneas and hypopneas and classify these***

Document ID:	SRC_SLE_Sparkle_PSG_2020_10908	Document title:		Classification:	Confidential
Modified:	26 July 2021	Clinical Investigation Protocol ICH E6 Aligned			
Version:	5	User Tool ID:	16.2.6UserTool0004		
Status:	Final	User Tool Version Date	5June2019	Page:	17

respiratory events as central, mixed, or obstructive. It is intended for adult use and can be used in a hospital, clinic, or patient home.

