12.1. Statistical Analyses

12.1.1. Sample Size Determination

The endpoint associated with Hypothesis 2 (ICC between PSG-CAI and DreamKit-CAI) exhibits a weaker effect size than the endpoint associated with Hypothesis 1 (ICC between PSG-AHI and DreamKit-AHI).

Pilot data from a sample of 178 records exhibited an ICC between the PSG-CAI and DreamKit-CAI 0.720 (95% CI 0.641 – 0.784). We will compare the lower-bound of the CI (0.641) to a threshold of 0.50, per Hypothesis 2. Assuming 90% power and an alpha of 0.05, $n=195$ participants will be required to test Hypothesis 2.

The same sample exhibited an ICC between the PSG-AHI and DreamKit-AHI of 0.908 (95% CI 0.879 – 0.931). We will compare the lower-bound of the CI (0.879) to a threshold of 0.75, per Hypothesis 1. Assuming 90% power and an alpha of 0.05, $n=56$ participants will be required to test Hypothesis 1. Thus, the sample size required for Hypothesis 2 ($n=195$) is more than adequate for Hypothesis 1, and we will adopt an overall sample size of $n=200$.

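### The exploratory apnea-differentiation kappa includes a no-event category, so it combines apnea detection with apnea typing and cannot by itself be read as typing agreement

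*Combined protocol and SAP*

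**What the plan says.** Section 4.3 lists "event-level differentiation of events" among the exploratory aims. Section 12.1.8, under event-level analyses, carries this out in two steps.

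- Detection: a "2x2 confusion matrix based on the presence/absence of events". An epoch staged as sleep on the PSG is positive "if it contains at least one respiratory event of any type", so hypopneas count as well as apneas.
- Typing: "We will construct a 4x4 confusion matrix based on apnea differentiation (obstructive apnea, central apnea, mixed apnea, no event", built by the same epoch method, with Cohen's kappa. For crowded epochs: "In cases where a single epoch contains more than one event, the first event will be used for categorization". If mixed events are too rare, "otherwise, mixed events will be placed in the obstructive category to create a 3x3 confusion matrix". The fallback merges two apnea types and keeps the no-event category.

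No statistic is named for the block of cells in which both systems score an apnea, or for the matrix collapsed to apnea versus no apnea. The analysis has no performance target. The typing evidence relates to the intended-use statement in section 4.4, under which the device detects apneas and hypopneas and classifies "respiratory events as central, mixed, or obstructive".

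**The concern.** Agreement that an epoch contains no apnea raises this kappa however well or badly the apneas are typed. Missed or extra apneas lower it even when every jointly scored apnea is typed correctly. A reader who takes the figure as agreement on obstructive, central or mixed type could be misled in either direction.

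The 2x2 analysis does not resolve this. It measures detection of any respiratory event, and a device can agree well on that while agreeing less well, or better, on apneas alone.

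The design makes the distinction worth keeping. Both systems share one nasal cannula (section 8.1.3) and both use Somnolyzer for respiratory events (section 8.1.5). Apneas are found from airflow but typed from respiratory effort, and effort is where the systems differ: PARE on the device, belts on the PSG. Shared airflow could raise detection agreement without testing the effort signal. That is plausible, not established: the PSG also records oronasal thermistry, and the documents do not say which airflow channel defines apneas.

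What is at stake is how clearly an exploratory result supports the classification wording in section 4.4. No formal test depends on it.

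**Working it through.** The plan states no expected or target kappa here, so there is no figure to reproduce. The check asks what typing agreement is compatible with a given overall kappa.

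**Assumed inputs (none is in the documents).** p0, the share of PSG-sleep epochs with no apnea on the PSG: 0.80, varied from 0.60 to 0.90; a = 1 − p0. Type mix q, obstructive/central/mixed: 60/30/10. Sensitivity (se) and specificity (sp) of device apnea detection against the PSG: three pairs. w: the typing kappa among epochs both systems score as an apnea. Missed and extra apneas are given the same type mix as the rest.

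**Cells.**
- PSG type i, device type j: a·se·[w·q_i·1(i=j) + (1−w)·q_i·q_j]
- PSG type i, device none: a·q_i·(1−se)
- PSG none, device type j: p0·(1−sp)·q_j
- Both none: p0·sp

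Kappa = (Po − Pe)/(1 − Pe). The margins do not depend on w, so the overall kappa is linear in w, running from k0 (w = 0) to k1 (w = 1). Hence w = (k − k0)/(k1 − k0).

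**Perfect detection, p0 = 0.80.** The sum of q² is 0.36 + 0.09 + 0.01 = 0.46.
- Po at w = 0: 0.80 + 0.20×0.46 = 0.892
- Pe: 0.64 + 0.04×0.46 = 0.6584
- k0 = 0.2336/0.3416 = 0.684; k1 = 1
- A reported kappa of 0.75 gives w = 0.066/0.316 = 0.21

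**90%/98%.** The device scores an apnea in 0.20×0.90 + 0.80×0.02 = 0.196 of epochs.
- Po at w = 0: 0.18×0.46 + 0.784 = 0.8668
- Pe: 0.20×0.196×0.46 + 0.80×0.804 = 0.6612
- k0 = 0.2056/0.3388 = 0.607; k1 = (0.964 − 0.6612)/0.3388 = 0.894
- w = 0.143/0.287 = 0.50. Check at w = 0.5: Po = 0.9154, kappa = 0.2542/0.3388 = 0.750

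**80%/97%.** The device scores an apnea in 0.184 of epochs.
- Po at w = 0: 0.16×0.46 + 0.776 = 0.8496; Pe = 0.6697
- k0 = 0.1799/0.3303 = 0.545; k1 = (0.936 − 0.6697)/0.3303 = 0.806
- w = 0.2054/0.2616 = 0.79

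| Detection (se/sp) | k0 | k1 | Typing kappa if overall kappa is 0.75 | Same, p0 from 0.60 to 0.90 | Apnea/no-apnea kappa, p0 = 0.80 |
|---|---|---|---|---|---|
| Perfect | 0.684 | 1.00 | 0.21 | 0.14–0.34 | 1.00 |
| 90%/98% | 0.607 | 0.894 | 0.50 | 0.50–0.59 | 0.89 |
| 80%/97% | 0.545 | 0.806 | 0.79 | 0.76–0.98 | 0.79 |

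The last column shows that the collapsed matrix tells the three cases apart.

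**Sensitivity to the assumptions at p0 = 0.80.**
- Type mix 45/45/10: the three readings become 0.27, 0.53 and 0.80.
- Type mix 80/15/5: random typing with perfect detection already gives an overall kappa of 0.80.
- 3x3 fallback with a 70/30 split: the readings are 0.00, 0.37 and 0.74.

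**A second set of assumptions** (mix 55/35/10, apnea in 5% to 30% of epochs). Chance typing with perfect detection gives an overall kappa of 0.64 to 0.71. Perfect typing with half the apneas missed and 3% false positives gives 0.46 to 0.57. At these extremes the overall kappa ranks the worse typist higher.

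**The case against.** The strongest reply is that the plan produces the confusion matrix as well as the kappa. Its apnea-by-apnea block shows typing, and the same table collapses to apnea versus no apnea. Reading a kappa of 0.75 backwards describes someone given the kappa without its table. This largely stands, and it narrows the point to the absence of a named statistic for cells that will exist anyway. Naming one in advance still helps, because a sub-block kappa chosen after the results are seen would be post hoc.

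A reader might infer that the plan has no event-level means of separating typing from detection, or that this kappa is its only event-level view of typing. The documents do not support either inference: the planned matrix is itself such a view and contains both components.

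A combined measure also suits section 4.4, which claims both detection and classification, and counting missed apneas is legitimate. That stands, and it is why the overall kappa should be kept. The section even lists no event among the categories, so the content is not hidden.

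Other analyses bear on typing: the CAI ICC with its 0.50 bound, the ICCs of per-type totals, and the CAI diagnostic metrics at five thresholds. They reduce reliance on this kappa, but they compare participants, not the type given to each event.

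The scenario values are assumed, and the very low typing kappas are a floor, not a forecast. The pilot sample "exhibited an ICC between the PSG-CAI and DreamKit-CAI 0.720", which makes purely random typing unlikely, although a participant-level ICC does not establish event-level typing. The recruitment bands in section 8.1.6 (about 10% of the sample in each central band, about 17% in each obstructive band) also make the 80/15/5 mix a poor fit to this design.

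**Conclusion.** The point holds in limited form. The planned kappa measures detection and typing together, and its value cannot be turned into typing agreement without knowing apnea detection, which the any-event 2x2 does not give. In the illustration one value, 0.75, spans typing kappas from 0.21 to 0.79. Those sizes rest on assumed prevalence, type mix and detection. The mixing itself follows from the category list and does not depend on them.

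It would go too far to say that the kappa carries no information on typing: at a fixed detection level it rises linearly with typing agreement. A reader might also infer that weak typing could pass unnoticed into a formal conclusion. The documents do not support that: the analysis is exploratory with no threshold, and Hypotheses 1 and 2 use participant-level ICCs that it does not enter. Where hypopnea-only epochs are placed is a separate drafting question and adds no weight here. This is a low-priority reporting improvement.

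**What to change.** In section 12.1.8, keep the overall 4x4 (or 3x3) kappa and label it as combined detection-and-typing agreement. Pre-specify beside it, from the same matrix:

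1. Cohen's kappa and per-type agreement among PSG-sleep epochs that both systems score as an apnea (obstructive/central/mixed, or obstructive/central if mixed is merged), with a participant-level bootstrap 95% CI because epochs cluster within participants.
2. The matrix collapsed to apnea versus no apnea, with the number of apnea epochs scored by only one system.

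The cost is a few lines of SAP text and minor programming; no new data are needed. The downside is that the typing kappa is conditional on joint detection, so a system that scores only clear apneas could look better on it. The share of apnea epochs that drop out is [a(1−se) + p0(1−sp)]/[a + p0(1−sp)]. With p0 = 0.80 this is 0.036/0.216 = 17% at 90%/98% and 0.064/0.224 = 29% at 80%/97%; over p0 from 0.60 to 0.90 the ranges are 13–24% and 23–37%. The typing kappa must therefore be read with that count and the overall kappa.
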